8.1 General Conventions

Subject data will be summarized in tables and further details will be provided in listing. All eCRF data will be listed per subject for all subjects. Descriptive statistical analyses will be provided for pre-specified study endpoints. Summaries for continuous variables will include number of observations (n), mean, standard deviation, median, minimum, and maximum. Summaries for categorical variables will include total and counts for each category and their corresponding percentages.

Data recorded at the nominal visits will be presented in summary tables; however, unscheduled visits will not be included in summary tables. Listings will include both scheduled and unscheduled visits.

Analyses will be conducted using SAS software. During the course of programming of tables that are mocked up in this SAP, minor modifications may become necessary. Examples of these minor modifications include, but are not limited to, re-wording of a footnote, addition of a footnote, re-labeling of a column, or addition or removal of a column from a table or listing. In cases where modifications to tables or listings are not related to a change in statistical analysis methodology or conclusions that could be made on the originally proposed methodology, then no amendment of the SAP is necessary. Any final analyses that differ from what has been specified in this document will be identified within the final statistical output and documented within the clinical study report.

8.2 Disposition of Study Subjects

Subject disposition will be summarized by procedure group, procedure subgroup, and in total using counts and percentages. The number and percentage of subjects in the AES who completed, screen failed and discontinued will be tabulated along with the specific reasons for discontinuation.

8.3 Demographic, Vital Signs, and Surgical Characteristics

Summary statistics of subject demographics (age, sex, childbearing potential, race, and ethnicity) and vital signs (height, weight, and body mass index) will be presented by procedure group, procedure subgroup and in total. Background information (smoking history, ASA score) and pregnancy test result will be summarized in a similar manner. Listings will be presented for subject's inclusion/exclusion criteria, demographic, vital sign, and background information.

Background information for upper GI, lower GI, and gynecological will be summarized separately. A listing will be provided for background information of each procedure group.

Medical history will be summarized by Medical Dictionary for Regulatory Activities (MedDRA) system organ class and preferred term. A listing will be presented for medical history. Treatment history will be listed. Prior and concomitant medications and concomitant procedures will be listed only.

Surgical characteristics will be summarized by procedure group, procedure subgroup, and in total as collected on the following forms: blood transfusion, intra-operative data, vessel transected, prophylactic use of clips, grade 3 form, and grade 4 form.

8.4 Primary and Secondary Endpoints and Associated Hypotheses

8.4.1 Primary Endpoint and Associated Hypotheses

The primary performance endpoint in this study is the number and percentage of vessels where hemostasis (\leq Grade 3) is achieved using the ENSEAL X1 device. The hemostasis grading scale is defined as:

- Grade 1: no bleeding at transection site;
- Grade 2: minor bleeding at transection site, no intervention needed;
- Grade 3: minor bleeding at transection site, mild intervention needed, use of compression, basic energy devices (monopolar and/or bipolar device), and/or touchups with ENSEAL X1.
- Grade 4: significant bleeding (e.g., pulsatile blood flow, venous pooling) requiring intervention such as extensive coagulation or ligation with use of additional hemostatic measures (e.g., hemoclips, staples, sutures, fibrin sealants, other advanced energy products).

The primary performance endpoint will be summarized at the vessel transection level as multiple vessel transections per subject is expected; that is, the denominator for the primary endpoint will be the total number of vessel transections and the numerator will be the number of vessel transections where hemostasis (\leq Grade 3) is achieved.

The following hypothesis will be evaluated for the primary endpoint:

H₀:
$$p \le 87.5\%$$

H₁: $p > 87.5\%$

Where *p* is the percentage of transections achieving a Grade 3 or lower hemostasis rating and 87.5% is set as a performance goal for the lower bound of acceptable hemostasis. A 95% confidence interval will be calculated for *p* based on the proportion of vessel transections where Grade 3 or lower hemostasis is achieved using Clopper-Pearson's method and the lower limit of this confidence interval will be compared to 87.5% to evaluate the above hypotheses. A p-value will be determined based on an exact binomial test. Primary endpoint will be evaluated for the total sample. For procedure group and procedure subgroup 95% CI will be provided using Clopper-Pearson's method for proportion of vessel transections where Grade 3 or lower hemostasis is achieved.

8.4.2 Secondary Endpoints and Associated Hypotheses

No formal hypotheses are specified for the secondary endpoints of this study.

Counts and percentages will be provided for the following secondary endpoints:

• Categories of 5-point scale scores for various tasks completed by the ENSEAL X1 device (adhesion removal or division, lymphatics or tissue bundles divided, tissue grasping, tissue cutting, or tissue dissection). The scale will be a 5-point scale (very dissatisfied, dissatisfied, neither satisfied or dissatisfied, satisfied, or very satisfied) asking how

- satisfied the surgeon was with the use of the device for each of the tasks as collected on the "ENSEAL X1 Usage form in eCRF;
- Categories of hemostasis grading scale for each vessel transected; and
- Type, name, and number of additional hemostasis products required to achieved hemostasis for Grade 4 vessel transections.

Counts and percentages will also be provided for type, size, and number of vessels transected. Listing will be provided for ENSEAL X1 usage and vessel transected forms.

8.4.3 Summary of additional key data

Summary statistics will be presented for the following additional key data:

- Procedure duration;
- Use of any other energy device (basic [monopolar and traditional bipolar], advanced bipolar, ultrasonic) in primary procedure (type, name, and number of device and reason for use), if applicable;
- Overall assessment questionnaire of how device performed in various tasks for lower GI/large intestine resection and gynecological procedures;
- Surgeon questionnaire administered once per investigator;
- Task questionnaire after each lower GI/large intestine resection and gynecological procedure;
- Generator questionnaire after each procedure for each GEN11 used;
- Surgical procedure conducted;
- Hospital stay duration;
- Name and number of vessels that were transected, surgeon determination of diameter size range (< 3 mm, 3 to 5 mm, and > 5 to 7 mm);
- Occurrence and location of cancer and occurrence of pre-surgical radiation/chemotherapy within 90 days prior to surgery, if applicable;
- Occurrence of vessel skeletonization;
- Presence of inflamed tissue, calcified tissues/vessels, atherosclerotic tissue, fibrotic tissue, or presence of adhesions, if applicable;
- Volume of estimated intra-operative blood loss;
- Occurrence of blood transfusion, if applicable (record the total required units of blood and rationale);
- Type of additional mild interventions (use of compression, basic energy devices [monopolar and/or bipolar] and/or touch-ups with ENSEAL X1) required to achieve hemostasis for Grade 3 vessel transections including number of times when ENSEAL X1 touch-ups were used; and
- Protocol deviation

Listing will be provided for task questionnaire, surgeon questionnaire, generator questionnaire, and protocol deviation,

8.5 Safety Analyses

The primary safety endpoint in this study is the occurrence of device-related adverse events (AEs). As per the study protocol, device-related AEs are those identified as having a relationship of possibly, probably, or causally with the ENSEAL X1 or GEN11 devices. AEs unrelated to the study device are recorded as 'not related' on the CRF. Both device-related and procedure-related AEs reported during the study will be coded to MedDRA. All reported AEs will be summarized by MedDRA system organ class and preferred term by procedure group, procedure subgroup, and in total. Separate summarizes will be provided for device-related and procedure-related AEs. Serious AEs will be summarized in a similar manner. All safety endpoints will be summarized by procedure group, procedure subgroup, and in total. All reported adverse events will be listed. Listings will also be provided for blood transfusion details, concomitant procedures, and concomitant medications.

Safety endpoints are as follows:

- All AEs
- Serious AEs
- All AEs related to the study device
- Serious AEs related to the study device
- All AEs related to the study procedure
- Serious AEs related to the study procedure

8.5.1 Safety Outcomes Reported in the CER

Safety outcomes identified in the CER # SCN060262 (ref. Table 33) will be summarized by procedure group, procedure subgroup, and in total. Only key safety outcomes that include major bleeding as defined as hemorrhage > 400 mL and thermal damage/injury will be presented. The observed event rates for the key safety outcomes from current study will be presented along with the median event rates from the CER for descriptive comparison. No statistical test will be conducted.

8.6 Plans for Interim Analysis

No interim analyses are planned for this study.

8.7 Handling of Missing Data

All summaries will be performed for enrolled subjects only and with observed data. There will be no imputation of data for early terminated subjects or for missing data within the database.

8.8 Sensitivity Analyses

The analysis of the primary performance endpoint described above in Section 8.4.1 makes the assumption of independence of activations within a subject in estimating the variance for the confidence interval. Achieving hemostasis (\leq Grades 3) may be correlated within a patient for those with two or more vessel transections. To account for the potential dependence in achieving

hemostasis in vessels within a subject, a sensitivity analysis will be performed where the 95% confidence interval will be estimated using a generalized linear mixed model. The underlying distribution of the dependent variable in the model is logistic as the outcome variable is binary (i.e., hemostasis achieved or not achieved). A random intercept term at subject-level will be used in the generalized linear mixed model to account for the within subject correlation in achieving hemostasis. The distribution of the random intercept is assumed to be Gaussian.

If the inference from the mixed model is not consistent with the inference from the primary endpoint analysis as described in Section 8.4.1 then the inference from the mixed model will be used to evaluate success.

Example SAS code:

*Create a pseudo variable group so that the 95% CI for intercept can be estimated;
data mydata; set mydata; group="pseudo"; run;

PROC GLIMMIX DATA = mydata;
CLASS id group;
MODEL OUTCOME (Event='0') = group / S DIST=BINARY LINK=LOGIT;
RANDOM intercept / SUBJECT = id;
LSMEANS group / CL ILINK; *The results of interest (95% CI of rate of hemostasis) are presented on the last two columns;
RUN;

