5.4 PRIMARY AND SECONDARY ENDPOINTS AND ASSOCIATED HYPOTHESES

All study endpoints are described in Section 2.1 through Section 2.4. The following hypothesis will be evaluated for the primary endpoint:

H₀: $p \le 87.5\%$

 H_1 : p > 87.5%

Where *p* is the percentage of transections achieving a Grade 3 or lower hemostasis rating and 87.5% is set as a performance goal for the lower bound of acceptable hemostasis. A 95% confidence interval will be calculated for *p* based on the sample proportion of transections where Grade 3 or lower hemostasis was achieved using Clopper-Pearson's method and the lower limit of this confidence interval will be compared to 87.5% to evaluate the above hypotheses. A p-value will be determined based on exact binomial test.

Given that multiple transections per subject may occur, a sensitivity analysis will be performed using appropriate methods to account for the potential correlation among the outcomes of multiple transections within the same subject and procedure. Further details of this approach will be provided in the SAP.

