5.7 SAMPLE SIZE JUSTIFICATION

A sample size of at least 230 vessel transections is required to have a minimum of 90% power for rejecting the null hypothesis when the expected rate of Grade 3 hemostatic transections is at least 94.0% based on exact binomial test and a one-sided significance level of 0.025. The hemostatic transection grades for vessels are assumed to be independent within a subject and procedure.

In order to achieve a total of 230 vessel transections for analysis with a minimum of 27 vessel transections in each group (including 4 subgroups in upper GI procedure), a minimum of 133 subjects (a maximum of 149 subjects) will be enrolled in the study.

The original sample size of the study was based on the assumption of one vessel transection per subject. At the time of amendment 5 the number of transections per subject was estimated to be 1.9 on average. The primary endpoint and the study hypothesis are based on hemostasis of vessel transection; therefore, the number of subject to be enrolled was updated to ensure 230 vessel transections.

Given that the primary endpoint is being evaluated intra-operatively, it is not anticipated that there will be subject dropout prior to evaluating this endpoint, thus no adjustment or increase in subject enrollment is planned to account for dropout. A minimum of 27 vessel transections in each group (including 4 subgroups in upper GI procedure) is planned to attain optimum representation of each of the procedure groups to the whole study sample.

From a safety perspective on the pooled analysis of 133 subjects and in consideration of rare AEs that may occur (e.g., bleeding requiring blood product transfusion), for an event that has an incidence rate of, for example, 1%, then in a sample of 133 subjects, the probability of observing at least 1 event is 73.7% under a binomial probability model. Thus, this sample size provides a high probability of observing rare events if they do occur, and provides reasonable assurance to conclude that the likelihood of such AEs is less than 2.8% if they do

not occur based on the upper limit of an exact 95% confidence interval when 0 events out of 133 subjects are observed.

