5.9.4 Primary and Secondary Endpoint Analyses

The number and percentage of vessels where hemostasis is achieved (≤ Grade 3) will be summarized and an exact 95% confidence interval will be estimated for each procedure group, procedure subgroup, and in total based on Clopper-Pearson's method. The performance goal hypothesis will be tested as described in Section 5.4.

The analysis of primary endpoint is based on the assumption of independence of hemostatic grades within subject and procedure. This assumption of independence and its impact on the overall study conclusion will be evaluated through sensitivity analyses and will be described in SAP.

Counts and percentages will be provided for type, size, and number of vessels transected, as well as for the grading scale distribution for all vessels transected, number of times ENSEAL X1 touch-ups were required, incidence of requirement for additional measures to obtain hemostasis on vessels (other advanced energy devices or hemostatic measures), and 5-point scale scores for various tasks completed by the ENSEAL X1 device (adhesiolysis, lymphatics or tissue bundles divided, tissue grasping, tissue cutting, or tissue dissection).

All device-related and procedure-related AEs reported during the study will be coded to MedDRA. All AEs will be summarized by MedDRA system organ class and preferred term by procedure group, procedure subgroup, and in total. Separate summaries will be provided for device-related and procedure-related AEs. Serious AEs will be summarized in a similar manner.

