All Enrolled Set: The All Enrolled Set (AES) contains all subjects who provide informed consent for this study. The AES will be used for disposition of study subjects and for all listings.

7 Sample Size Justification

A sample size of at least 230 vessel transections is required to have a minimum of 90% power for rejecting the null hypothesis when the expected rate of Grade 3 hemostatic transections is at least 94.0% based on exact binomial test and a one-sided significance level of 0.025. The hemostatic transection grades for vessels are assumed to be independent within a subject and within a procedure.

In order to achieve a total of 230 vessel transections for analysis with a minimum of 27 vessel transections in each group (including 4 procedure subgroups in upper GI procedure), a minimum of 122 subjects (a maximum of 149 subjects) will be enrolled in the study.

The original sample size of the study was based on the assumption of one vessel transection per subject. At the time of amendment 5 the number of transections per subject was estimated to be 1.9 on average. The primary endpoint and the study hypothesis are based on hemostasis of vessel transection; therefore, the number of subject to be enrolled was updated to ensure 230 vessel transections.

Given that the primary endpoint is being evaluated intra-operatively, it is not anticipated that there will be subject dropout prior to evaluating this endpoint, thus no adjustment or increase in subject enrollment is planned to account for dropout. A minimum of 27 vessel transections in each group (including 4 procedure subgroups in upper GI procedure) is planned to attain optimum representation of each of the procedure groups to the whole study sample.

From a safety perspective on the pooled analysis of 133 subjects and in consideration of rare AEs that may occur (e.g., bleeding requiring blood product transfusion), for an event that has an incidence rate of, for example, 1%, then in a sample of 133 subjects, the probability of observing at least 1 event is 73.7% under a binomial probability model. Thus, this sample size provides a high probability of observing rare events if they do occur, and provides reasonable assurance to conclude that the likelihood of such AEs is less than 2.8% if they do not occur based on the upper limit of an exact 95% confidence interval when 0 events out of 133 subjects are observed.

8 Analyses to be Conducted

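### SAP 8.8 lets the mixed model overrule the primary exact test in either direction, so a failed exact test can become a success

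*SAP*

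**What the plan says.** - **Hypothesis.** In SAP 8.4.1, p "is the percentage of transections achieving a Grade 3 or lower hemostasis rating and 87.5% is set as a performance goal". H0 is p ≤ 87.5%.
- **Primary decision.** In Protocol 5.4, "the lower limit of this confidence interval will be compared to 87.5% to evaluate the above hypotheses", where the interval is Clopper-Pearson. SAP 8.4.1 repeats this and adds: "A p-value will be determined based on an exact binomial test".
- **Clustering.** Protocol 5.4 announces a sensitivity analysis for correlation within subject and leaves the method to the SAP. Protocol 5.9.4 says: "This assumption of independence and its impact on the overall study conclusion will be evaluated through sensitivity analyses and will be described in SAP". Neither section says that this analysis replaces the primary one.
- **Override.** SAP 8.8 specifies a logistic mixed model with a Gaussian random intercept per subject. If its inference is inconsistent with that of Section 8.4.1, "then the inference from the mixed model will be used to evaluate success". The example code takes its interval from LSMEANS with ILINK and comments: "The results of interest (95% CI of rate of hemostasis) are presented on the last two columns".
- **Power.** SAP 7 says: "A sample size of at least 230 vessel transections is required to have a minimum of 90% power for rejecting the null hypothesis", by the exact test at one-sided 0.025. Protocol 5.7 states the condition: "The hemostatic transection grades for vessels are assumed to be independent within a subject and procedure".

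**The concern.** The override names no direction, sets no requirement that both analyses pass, and does not say what happens if the model fails to converge. A reader of Protocol 5.4 would take the exact test as the criterion. Under SAP 8.8 it has no independent role once the model gives a result.

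The deciding limit also belongs to a different quantity from the p in H0. For success rates near 90%, that quantity tends to rise above p as subjects differ more from one another. An adjustment meant to protect against clustering can therefore make success easier as clustering grows. At stake is the study's only formal hypothesis: it could be declared met after the exact test failed, with no power or error rate given for the rule that decides.

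**Working it through.** **1. The plan's own figure.** Inputs from SAP 5, 7 and 8.4.1: null rate 0.875, expected rate 0.94, one-sided 0.025, n = 230. The smallest r with P(X ≥ r | 230, 0.875) ≤ 0.025 is 212. Size is 0.0161 and power is P(X ≥ 212 | 230, 0.94) = 0.9002, so the stated 90% reproduces. At 133 × 1.9 ≈ 253 vessels the cut-off is 232, size 0.0226 and power 0.9470. All of this describes the exact test under independence.

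**2. The decision rule as written.**

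| Exact test | Mixed model | Outcome under SAP 8.8 |
|---|---|---|
| pass | pass | success |
| pass | fail | failure (model used) |
| fail | pass | success (model used) |
| fail | fail | failure |

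The outcome column equals the model column in every row. This reads the model's inference as its lower 95% limit against 87.5%, which SAP 8.8 implies but does not state.

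**3. The quantity estimated.** With random intercept u ~ N(0, σ²), the proportion in H0 is p = E[expit(β₀ + u)]. LSMEANS/ILINK returns expit(β₀). Solving for p = 0.875:

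- σ = 0.97 (ICC about 0.1): β₀ = 2.267, expit(β₀) = 0.906
- σ = 1.97 (ICC about 0.3): β₀ = 3.033, expit(β₀) = 0.954

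Here ICC = (E[π²] − p²)/[p(1 − p)], with π = expit(β₀ + u). The default fit reaches these values only in part: its median estimate in simulation was 0.878 and 0.884.

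**4. Worked example.** Assume 133 subjects, 36 with one vessel and 97 with two (36 + 2 × 97 = 230), and 211 successes, so p̂ = 0.9174. The exact lower limit is 0.8740 (p = 0.0277), a failure. Let D subjects fail on both vessels, with the other failures spread over single- and two-vessel subjects in proportion to vessels.

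- Model limit: residual pseudo-likelihood (taken as the procedure default, since the code names no method), expit(β̂₀ − t·SE), with 230 − 133 = 97 df.
- Cluster-robust limit for p: expit(logit p̂ − t₁₃₂·SE), with SE = √[(133/132)·Σᵢ(Σⱼ(yᵢⱼ − p̂))²] / [230·p̂(1 − p̂)].

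For D = 4 there are 9 two-vessel subjects with one failure and 2 single-vessel failures:

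- Model: β̂₀ = 2.535, SE = 0.2729; 2.535 − 1.985 × 0.2729 = 1.993, giving 0.8801.
- Robust: the sum of squares is 23.95, so SE = √(1.0076 × 23.95)/17.43 = 0.2818; 2.407 − 1.978 × 0.2818 = 1.850, giving 0.8641.

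| D | Model lower limit | Cluster-robust lower limit for p |
|---|---|---|
| 0 | 0.8735 | 0.8755 |
| 1 | 0.8729 | 0.8724 |
| 2 | 0.8743 | 0.8697 |
| 3 | 0.8769 | 0.8669 |
| 4 | 0.8801 | 0.8641 |
| 6 | 0.8877 | 0.8590 |

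From D = 3 upward the model turns the failed exact test into a success. From D = 1 the two limits move in opposite directions.

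**5. How often.** The documents give no within-subject correlation, so a range is assumed. Simulation used a logit-normal model, 133 subjects, a true rate of 87.5% and 8000 replicates (Monte Carlo SE about 0.17 points at 2.5%).

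| | ICC 0 | 0.1 | 0.2 | 0.3 |
|---|---|---|---|---|
| 230 vessels: exact test alone, % | 1.7 | 2.1 | 2.4 | 2.9 |
| 230 vessels: SAP 8.8 rule, % | 1.8 | 2.4 | 3.0 | 4.2 |
| 230 vessels: fail to success, % | 0.04 | 0.26 | 0.61 | 1.25 |
| 253 vessels: exact test alone, % | 2.5 | 3.1 | 3.6 | 4.4 |
| 253 vessels: SAP 8.8 rule, % | 2.4 | 2.8 | 3.7 | 5.1 |
| 253 vessels: fail to success, % | 0.02 | 0.08 | 0.45 | 1.09 |

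Success-to-fail reversals were at most 0.01% with 230 vessels and 0.14% to 0.41% with 253. Beta-binomial data (230 vessels) gave fail-to-success rates of 0.17% at ICC 0.1 and 0.98% at ICC 0.3.

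**The case against.** **The rule is prespecified and the protocol delegates it.** True. Protocol 5.4 and 5.9.4 leave the method to the SAP and foresee an effect on the conclusion, so this is not a post hoc rescue. But delegating the method does not settle the direction of an override, and prespecification does not turn the estimated quantity into p.

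**The inflation is modest.** This stands as a limit on size. With 230 vessels the total stays within 2.5% up to ICC 0.1 and exceeds it from about 0.2. With 253 vessels the rule adds to the exact test's error only at ICC 0.3. Part of the excess comes from the exact test itself ignoring clustering.

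**The example is chosen at the edge.** 211 is one success short of the cut-off. With 0, 1 or 2 double failures the model agrees with the exact test, and three or more would be unusual without clustering. It shows that the reversal can happen and which way the limit moves; the simulation shows how often.

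**The figures are not SAS output.** They come from Python re-implementations. Quadrature behaves very differently: for 211/230 with four double failures and 121 subjects, one fit gave 0.8942 by quadrature and 0.8798 by pseudo-likelihood, and success-to-fail reversals became common. At a true rate of 94% (133 subjects, 230 vessels) the model failed to converge in 0.1/1.7/5.1/11.8% of runs at ICC 0/0.1/0.2/0.3; those runs were scored by the exact test, which the SAP does not specify. This limits the precision of the rates. It also shows that the deciding rule is not fully defined.

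**The remedy costs power.** It does, and the cost is set out with the fix.

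**Conclusion.** The concern holds and should be corrected before the analysis. That the model decides alone follows from the wording of SAP 8.8 and needs no simulation. That its limit does not refer to p follows from the LSMEANS/ILINK code.

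The frequency depends on the assumed ICC, the vessels per subject (the documents give only the mean of 1.9) and the estimation method. Under the default method, fail-to-success reversals at the null range from 0.04% to 1.25% with 230 vessels. With little clustering the two analyses almost always agree. The 230 vessels and 90% power are correct for the exact test, but they do not describe the rule that decides success.

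**What to change.** Replace the override sentence in SAP 8.8 with:

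> Success requires the Clopper-Pearson lower limit to exceed 87.5% (Section 8.4.1). If the cluster-adjusted lower limit for the marginal proportion of transections does not also exceed 87.5%, success will not be claimed. The cluster-adjusted analysis cannot convert a failed primary analysis into a success. The cluster-adjusted limit comes from an intercept-only GEE (logit link, independence working correlation, subject as cluster, robust variance, t with number of subjects minus 1 degrees of freedom). If no failure is observed, the Clopper-Pearson limit alone applies. The mixed model is reported descriptively; its non-convergence is reported and does not affect success.

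Align Protocol 5.4 and 5.9.4 with this rule. State in SAP 7 that the 90% power does not cover the added requirement.

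The work is wording and a few lines of code. The statistical cost at a true rate of 94% with 133 subjects is:

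| Chance of success, % | ICC 0 | 0.1 | 0.2 | 0.3 |
|---|---|---|---|---|
| Current rule, 230 vessels | 90.2 | 90.2 | 90.5 | 91.5 |
| Proposed rule, 230 vessels | 89.5 | 85.9 | 81.1 | 76.7 |
| Proposed rule, 253 vessels | 93.4 | 89.5 | 84.6 | 79.5 |

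With 230 vessels, removed fail-to-success reversals account for 0.1/1.5/3.3/4.5 points of the loss; the rest is the price of a limit that reflects clustering. At ICC 0.3 that is 91.5 − 76.7 = 14.8 points in all, of which 10.3 are that price. False success under the proposed rule was 1.4% to 2.4% in all 18 null scenarios run, up to ICC 0.3; stronger clustering was not examined.

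The sentence barring conversion of a failed primary analysis is the minimum change. Taken alone, with the mixed model kept as the second condition, it would leave false success at 2.9% (230 vessels) or 4.0% (253 vessels) at ICC 0.3.
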